3.2 Exclusion Criteria

The subject must be excluded from participating in the trial if the subject:

- 3.2.1. Has received any second-line systemic therapy for advanced HCC after disease progression following sorafenib/lenvatinib therapy, or has had prior radiotherapy to the proposed treatment field (at the discretion of the Principal Investigators).
- 3.2.2. Is currently participating and receiving experimental treatment as part of a clinical trial, or has participated in a study of an immune checkpoint inhibitor and received study therapy, or used an investigational device within 4 weeks of the first dose of treatment.
- 3.2.3. Has had a previous solid organ transplant, a diagnosis of immunodeficiency, or is receiving systemic steroid therapy or any other form of immunosuppressive therapy within 7 days prior to the first dose of trial treatment.
- 3.2.4. Has liver tumor not amenable to SBRT, as per 3.1.5 above, or has had prior upper abdominal radiation therapy within planned volumes (exceeding standard tolerances).
- 3.2.5. Has a histological or cytological diagnosis of fibrolamellar HCC, sarcomatoid HCC, or mixed cholangiocarcinoma-HCC.
- 3.2.6. Has had prior radioembolization or other selective internal radiotherapy treatment to the liver.
- 3.2.7. Has dual active HBV infection (HBsAg (+) and/or detectable HBV DNA) and HCV infection (anti-HCV Ab(+) and detectable HCV RNA) at study entry.
- 3.2.8. Has had esophageal or gastric variceal bleeding within 3 months prior to study enrollment.
- 3.2.9. Has had encephalopathy in the past 6 months, or has clinically apparent ascites at the time of study enrollment.
- 3.2.10. Has a known history of active TB (Bacillus Tuberculosis).

- 3.2.11. Hypersensitivity to pembrolizumab or any of its excipients.
- 3.2.12. Has had prior chemotherapy, targeted small molecule therapy, or radiation therapy within 1 week prior to study Day 1 or who has not recovered (i.e., \leq Grade 1 or at baseline) from adverse events due to a previously administered agent.
 - Note: Subjects with \leq Grade 2 neuropathy are an exception to this criterion and may qualify for the study.
 - Note: If subject received major surgery, they must have recovered adequately from the toxicity and/or complications from the intervention prior to starting therapy.
- 3.2.13. Has a known history of prior invasive malignancy except if the subject has undergone curative-intent therapy with no evidence of disease recurrence for 2 years prior to study entry. Exceptions include basal cell carcinoma of the skin, squamous cell carcinoma of the skin, superficial bladder cancer, low-risk prostate cancer or in situ cervical cancer.
- 3.2.14. Has known active central nervous system (CNS) metastases and/or carcinomatous meningitis. Subjects with previously treated brain metastases may participate provided they are stable (without evidence of progression by imaging for at least four weeks prior to the first dose of trial treatment and any neurologic symptoms have returned to baseline), have no evidence of new or enlarging brain metastases, and are not using steroids for at least 7 days prior to trial treatment. This exception does not include carcinomatous meningitis which is excluded regardless of clinical stability.
- 3.2.15. Has active autoimmune disease that has required systemic treatment in the past 2 years (i.e. with use of disease modifying agents, corticosteroids or immunosuppressive drugs). Replacement therapy (e.g. thyroxine, insulin, or physiologic corticosteroid replacement therapy at a dose of \leq 10 mg/day of prednisone or equivalent) is not considered a form of systemic treatment.
- 3.2.16. Has known history of, or any evidence of active, non-infectious pneumonitis/interstitial lung disease.
- 3.2.17. Has an active infection requiring systemic therapy.
- 3.2.18. Has a history or current evidence of any condition, therapy, or laboratory abnormality that might confound the results of the trial, interfere with the subject's participation for the full duration of the trial, or is not in the best interest of the subject to participate, in the opinion of the treating investigator.
- 3.2.19. Has known psychiatric or substance abuse disorders that would interfere with cooperation with the requirements of the trial.
- 3.2.20. Is pregnant or breastfeeding, or expecting to conceive or father children within the projected duration of the trial, starting with the pre-screening or screening visit through 120 days after the last dose of trial treatment.

- 3.2.21. Has received prior therapy with an anti-PD-1, anti-PD-L1, or anti-PD-L2 agent.
- 3.2.22. Has a known history of Human Immunodeficiency Virus (HIV) (HIV 1/2 antibodies).
- 3.2.23. Has alcohol related or non-alcoholic steatohepatitis (NASH) related cirrhosis.
- 3.2.24. Has had a history of significant active or unstable heart disease
- 3.2.25. Has received a live vaccine or live-attenuated vaccine within 30 days of planned start of study therapy. Administration of killed vaccines is allowed.

3.3 Inclusion of Women and Minorities

Both men and women of all races and ethnic groups are eligible for this trial. This study is designed to include minorities as appropriate. However, the trial is not designed to measure differences in intervention effects. The population of Southern Ontario is ethnically diverse and the proportion of different ethnic groups in the community is provided in the table below. Universal access to health care will ensure that there is no discrimination on the basis of race or gender (Guide to Canadian Human Rights Act: www.chrc-ccdp.ca/public/guidechra.pdf). Individual hospital registries and databases do not routinely collect racial data, under the direction of the Canadian Human Rights Code.

4. REGISTRATION PROCEDURES

4.1 General Guidelines

The Central Office Coordinator at the Drug Development Program Central Office will enter eligible subjects on study centrally. All sites should call the Central Office Coordinator (listed on cover page) to verify dose level availabilities. The required forms (Registration Checklist) will be provided upon site activation.

Following registration, subjects should begin protocol treatment within 7 days. Issues that would cause treatment delays should be discussed with the Principal Investigator (cc the Central Office Coordinator). If a subject does not receive protocol therapy following registration, the subject's registration on the study may be cancelled. The Central Office Coordinator should be notified of cancellations as soon as possible.

4.2 Registration Process

Prior to registering a subject, each institution must have submitted all necessary regulatory documentation to the Drug Development Program Central Office. The registration checklist will only be sent once this has been received.

No subject can receive protocol treatment until registration with the Central Office has taken place. All eligibility criteria must be met at the time of registration. There will be no exceptions. Any questions should be addressed with the Central Office prior to registration.

To register a subject, the following documents are to be completed by the research nurse or data

manager and sent / faxed to the Central Office Coordinator:

- Signed subject consent form
- Registration Checklist CRF signed by the investigator

To complete the registration process, central office will review the checklist and once eligibility has been confirmed:

- Assign a subject study number
- Assign the subject a dose
- Register the subject on the study
- Fax or e-mail the confirmation worksheet with the subject study number and dose to the participating site

To ensure immediate attention is given to the faxed checklist, each site is advised to also call the Central Office Coordinator listed on the front sheet. Subject registration will be accepted between the hours of 9am to 5pm Monday to Friday, excluding Canadian statutory holidays when the central office will be closed.

5. TREATMENT PLAN

5.1 Agent Administration

Treatment will be administered on an outpatient basis. Appropriate dose delays and management of adverse events are described in Section 6. No investigational or commercial agents or therapies other than those described below may be administered with the intent to treat the subject's malignancy.

Regimen Description			
Agent	Dose	Route	Schedule
Pembrolizumab	200 mg	IV over 30 minutes	Every 3 weeks
SBRT administered to dominant hepatic HCC			Starting day 2 of cycle 1 pembrolizumab, given in 5 fractions over 5-15 days

5.1.1 Pembrolizumab Dose Selection

The rationale for selection of the dose to be used in this trial is provided in Section 2.2.1.3 Rationale for Dose Selection.

5.1.1.1 Timing of Dose Administration

Trial treatment should be administered on Day 1 of each cycle after all procedures/assessments have been completed as detailed in the STUDY CALENDAR (Section 10). Trial treatment may be administered up to 1 day before or 3 days after the scheduled Day 1 of each cycle due to administrative reasons.

All trial treatments will be administered on an outpatient basis.

In general, toxicities from previous cycles of treatment should have returned to Grade 0-1 before the next dose of study medication (see Section 6.1 for specific guidance). Pre-existing Grade 2 toxicities, which did not result in exclusion from the trial, (for example, liver transaminase abnormalities) should be stable.

Pembrolizumab 200 mg will be administered as a 30 minute IV infusion every 3 weeks. Every effort should be made to target infusion timing to be as close to 30 minutes as possible. However, given the variability of infusion pumps from site to site, a window of -5 minutes and +10 minutes is permitted (i.e., infusion time is 30 minutes: -5 min/+10 min).

The Pharmacy Manual contains specific instructions for the preparation of the pembrolizumab infusion fluid and administration of infusion solution.

5.1.2 Stereotactic Body Radiotherapy (SBRT) Dosing and Scheduling

All the definite HCC with vascular invasion should be treated by SBRT when safe, up to a maximum of 10 lesions and total diameter of ≤ 20 cm. However, extrahepatic HCC, all satellites of HCC and non-definite HCC need not be encompassed within the irradiated volumes, especially if normal tissue dose limits cannot be met.

Treatment will be delivered in 5 fractions. The time between fractions should be between 24 and 72 hours, with treatment delivered to all targets over 5 to 15 days (starting on day 2, as per the schema). The preferred inter-fraction interval is 24 hours, with the exception of when luminal OARs are at their maximal dose, when it is preferred that the first two fractions are to be delivered on day 2 and 3 and other fractions every other day. All lesions may be treated on the same day, or alternative lesions may be treated on alternate days, as long as the overall treatment time is 15 days at maximum.

5.1.2.1 Prescription Dose

Absorbed dose: 27.5 Gy - 50 Gy in 5 fractions. The prescription dose may be 50 Gy, 45 Gy, 40 Gy, 35 Gy, 30 Gy or 27.5 Gy in 5 fractions, based on normal tissue constraints. The dose to multiple PTVs may be different. The goal is to use the highest allowable prescription dose to the primary target, while respecting normal tissue constraints. The minimal planned prescription dose to PTVs is 27.5 Gy. Given the novelty of this combination, and the potential for overlapping hepatic toxicity, the first 10 patients will have to meet all the following additional liver dosimetric constraints:

- 1) Mean liver (minus gross HCC tumor volume) dose < 15 Gy in 5 fractions.
- 2) $D_{800cc} \leq 18$ Gy in 5 fractions
- 3) Biologically corrected normal tissue complication probability (NTCP) $< 0.5\%$

If 2 or fewer patients of the first 10 patients experience grade 3 hepatic toxicity at this dose, we will increase to standard dosing. If 3 or more patients experience grade 3 toxicity, or if any patients experience grade 4/5 toxicity in first 3 months following SBRT, these dose constraints will be maintained for all patients on study and modification of all SBRT dose constraints will be considered.

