A phase III study of 799 patients treated with palliative radiation therapy (8 Gy in 1 fraction) for bone metastases from prostate cancer (CA184-043) reported grade 3/4 toxicity in 26% versus 3% in patients treated with radiation followed by ipilimumab or placebo respectively, consistent with reported toxicity from ipilimumab alone.⁵⁸ In a phase I study of 35 patients treated with Ipilimumab and SBRT (50 Gy in 4 fractions), 2 patients treated with concurrent SBRT and ipilimumab developed dose limiting toxicity (grade 3 pancreatitis and lipase elevation); one patient with sequential ipilimumab and SBRT developed grade 3 increase in bilirubin and AST, and 12 of 35 patients (34%) had grade 3 toxicity (colitis in 4), slightly higher than reported grade 3 toxicity post ipilimumab alone (10 – 28%) with no grade 4 or 5 toxicity observed.⁵⁹ Clinical benefit was associated with increased peripheral CD8+ T cells, CD8+/CD4+ T cell ratio and proportion of CD8+ T cells expressing 4-1BB and PD-1. There was greater T cell activation in patients receiving liver SBRT versus lung SBRT. Another small study of ipilimumab with SBRT in metastatic melanoma reported responses in 6 of 22 evaluable patients, and manageable toxicity with only 3 patients discontinuing treatment due to adverse events, and grade 3/4 toxicity in 14% of patients.⁶⁰

In summary, there has not been a clear indication that toxicity is increased with the combination of

radiation and ICI, but there is a need for prospective data, especially in HCC.

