5.1.2.3 Dose Prescription

Is based on the volume of normal tissues irradiated (correlated with mean liver dose), as well as proximity of stomach, duodenum, small and large bowel (GI luminal structures) to the target volumes, as normal tissue constraints must be maintained in this study.

In the absence of adjacent GI luminal structures that may limit dose, the PTV dose prescription should be as high as possible based on mean liver dose (MLD, defined as the mean dose to the liver minus all GTVs), with 6 potential dose levels. Note, no variations in mean liver dose are permitted.

Table 2: SBRT Dose Prescription

Priority Constraint	Prescription Dose	
Allowed MLD (Gy)*	Planned Prescription Dose (Gy)	If the max allowed MLD is exceeded at this planned dose
13.0	50	Reduce to 45 Gy and re-evaluate
15.0	45	Reduce to 40 Gy and re-evaluate
15.0	40	Reduce to 35 Gy and re-evaluate
15.5	35	Reduce to 30 Gy and re-evaluate
16.0	30	Reduce to 27.5 Gy and re-evaluate
17.0	27.5	Ineligible

*< 15.0 Gy for the first 10 patients, regardless of prescription dose

- Vascular tumor thrombosis (e.g., portal vein thrombosis) dose should be treated to the same dose as the parenchymal HCC. However, lower doses are acceptable if required to maintain normal tissue limits, since the cancer density may be lower than parenchymal HCC. Non-tumor bland thrombosis is strongly recommended to NOT be irradiated, to reduce the overall volume irradiated.
- Maximum dose within PTV = 150%. If multiple PTVs exist, 150% of the maximal PTV prescription dose is permitted for all PTVs. Concomitant boost to the GTV to 1-2 dose levels above the prescription dose are recommended, and it is desirable to have a hot spot of at least 40 Gy in the GTV if possible.

- Maximum dose outside PTV = 120% of the maximal PTV prescription.
- Efforts should be made to keep the prescription dose and the 30Gy isodose as conformal as possible.
- Different isodoses may cover different PTVs. If multiple PTVs, the MLD should be evaluated with the prescription dose corresponding to the highest dose level that any PTV is treated. Queries should be directed to the study PI.

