If there is one kidney mean dose > 10Gy, remaining (or only) kidney V10Gy < 10%

The following organ dose constraints are strongly advised to be met, but are not mandatory:

Stomach (to 5 cc):	< 25 Gy
Duodenum (to 5 cc):	< 25 Gy
Small bowel (to 5 cc):	< 25 Gy
Liver minus all GTVs:	>700cc and D800cc ≤ 18 Gy
Heart max (30cc):	< 30 Gy
Skin (external) max (0.5 cc):	< 32 Gy
Chest wall max (0.5 cc):	< 50 Gy
Gallbladder max (0.5 cc):	< 55 Gy
Common bile duct max (0.5 cc)	< 50 Gy*

*Even though the bile duct is not often well visualized, it is always within the portal region and may be within high dose volumes for central targets, so efforts to reduce hot spots in this region are warranted.

Peer review of all SBRT plans is required prior to starting SBRT (either one-on-one or at GI or SBRT quality assurance rounds) by another radiation oncologist.

Treatment Interruptions

Treatment interruptions should be clearly documented in the patient’s treatment record. Total treatment time is recommended to be 10 days, with allowable total duration between 5 days and 15 days.

Total Treatment Duration

Per protocol: All treatment falls within 15 calendar days

Variation Acceptable: All treatments fall within 16 to 21 calendar days

Deviation Unacceptable: All treatments that take 22 or more calendar days to complete

PTV Dosimetry

Target coverage for each PTV should be considered on its own. If there are multiple tumors, the primary (dominant) PTV should be labeled #1. **The intent is for prescription dose to cover 95% of each PTV.**

If PTVs are not treated as per guidelines, this is a deviation unacceptable. The PTV should be treated to as high a dose as possible, respecting normal tissue constraints, as a dose response has been observed. Modifying required PTVs due to close proximity of adjacent OARs is not permitted.

The following **Table 3** describes variations and deviations in the prescription dose (dose covering 95% of the PTV). **Treating “per protocol” should always be the planning intent.**

Table 3: Variations and Deviations in Prescription Dose

Dose to 95% PTV	PTVs around GTVs*	PTVs around non-GTV CTVs*
Per protocol	Prescription dose +/- 5%	Prescription dose +/- 5%
Variation acceptable	90-95% or 105-110% of prescription dose, and ≥ 25 Gy	90-95% or 105-110% of prescription dose, and ≥ 25 Gy
Deviation unacceptable	<90% or >110% of prescription dose, or < 25 Gy	<90% or >110% of prescription dose, or < 25 Gy
Overall plan deviation unacceptable	< 25 Gy	

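### The rule for relaxing liver dose limits after the first 10 patients gives opposite instructions when grade 3 hepatic events are few but a grade 4/5 event occurs

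*Combined protocol and SAP*

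**What the plan says.** Section 5.1.2.1 adds three liver limits for the first 10 patients: mean liver dose below 15 Gy, D800cc of at most 18 Gy, and NTCP below 0.5%. The stated reason is "Given the novelty of this combination, and the potential for overlapping hepatic toxicity".

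Two consecutive sentences then decide what happens to later patients:

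- Sentence 1: "If 2 or fewer patients of the first 10 patients experience grade 3 hepatic toxicity at this dose, we will increase to standard dosing".
- Sentence 2: "If 3 or more patients experience grade 3 toxicity, or if any patients experience grade 4/5 toxicity in first 3 months following SBRT", then "these dose constraints will be maintained for all patients on study". It adds that changes to the SBRT constraints as a whole will be considered.

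The footnote to Table 2 (Section 5.1.2.3) repeats the mean-liver-dose limit, "15.0 Gy for the first 10 patients, regardless of prescription dose", without a decision rule. Section 7.9 describes the DSMB's general safety review and does not mention this rule. The interim analysis in Section 13.3 concerns response only.

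**The concern.** This is the protocol's only explicit rule for releasing later patients from the extra liver limits, and its two sentences are not mutually exclusive. Sentence 1 makes no exception for grade 4/5 events. Suppose one patient has grade 4 hepatic toxicity and nobody has grade 3. Sentence 1 then calls for standard dosing and sentence 2 for keeping the limits. No section says which prevails.

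The wording has a second mismatch. Sentence 1 counts grade 3 *hepatic* toxicity; sentence 2 counts grade 3 toxicity without the qualifier. Taken literally, three patients with grade 3 colitis and no liver event would also satisfy both sentences.

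At stake is whether patients after the tenth are planned under looser liver limits following a severe event in a combination whose hepatic risk the protocol itself flags.

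**Working it through.** The documents state no operating characteristic for this rule, so there is no figure to reproduce. The check is logical.

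**Notation.** Among the first 10 patients, let H be the number with grade 3 hepatic toxicity, T the number with grade 3 toxicity as counted in sentence 2, and S the number with grade 4/5 toxicity within 3 months of SBRT.

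- Sentence 1: H ≤ 2 → increase.
- Sentence 2: T ≥ 3 or S ≥ 1 → maintain.

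**Step 1: assume sentence 2 also means hepatic (T = H).**

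| | S = 0 | S ≥ 1 |
|---|---|---|
| H ≤ 2 | increase | **increase and maintain** |
| H ≥ 3 | maintain | maintain |

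One cell conflicts and none is empty. The conflict does not depend on whether grade 3 means exactly grade 3 or grade 3 and above. One patient with grade 4 hepatic toxicity and no other event gives a grade 3 count of 0 or 1, both at most 2, with S = 1.

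**Step 2: which sentence can prevail?** If sentence 1 prevails, H ≤ 2 gives an increase whatever S is, and H ≥ 3 gives maintenance whatever S is. S then never affects the decision. If sentence 2 prevails, S decides the upper right cell. Only the second reading gives the grade 4/5 condition any effect.

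**Step 3: take sentence 2 literally, as any organ.** T can exceed H. With H = 0, T = 3 and S = 0, sentence 1 says increase and sentence 2 says maintain, with no grade 4/5 event.

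**Step 4: what an increase would change.**

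| Limit | First 10 patients (5.1.2.1) | Standard dosing |
|---|---|---|
| D800cc ≤ 18 Gy | mandatory | advisory (5.1.2.6: "The following organ dose constraints are strongly advised to be met, but are not mandatory") |
| NTCP < 0.5% | mandatory | no limit stated |
| Mean liver dose at 35 Gy | < 15 Gy | 15.5 Gy (+0.5) |
| Mean liver dose at 30 Gy | < 15 Gy | 16 Gy (+1.0) |
| Mean liver dose at 27.5 Gy | < 15 Gy | 17 Gy (+2.0) |

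At 50, 45 and 40 Gy, Table 2 allows 13, 15 and 15 Gy, so the mean-dose cap is not effectively loosened.

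**Step 5: does a corrected rule close the gap?** Let increase apply only if H ≤ 2 and S = 0, with maintain otherwise. Classify each patient by worst grade and treat grade 3 as hepatic. Ten patients then give 66 possible pairs (H, S). As written, 3 pairs satisfy sentence 1 only, 36 sentence 2 only, and 10 + 9 + 8 = 27 both (H = 0, 1, 2 with S ≥ 1); 3 + 36 + 27 = 66. Under the corrected rule 3 pairs lead to an increase, 63 to maintenance and none to both. These counts check completeness; they are not probabilities.

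**The case against.** The best defence is that the text settles precedence by implication. As step 2 shows, letting sentence 1 win empties the grade 4/5 condition of meaning, and the override reading is also the cautious one. The missing *hepatic* is probably ellipsis: 2 or fewer and 3 or more are natural complements, in a paragraph about liver limits and hepatic risk. The 3-month window can likewise be read as governing both sentences. If sentence 2 were applied to any organ, the result would be tighter liver limits, which is the safer direction for the liver.

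The practical reach is also limited. One participating institution is listed, so this is a single decision. Serious events reach the Central Office within 24 hours, the DSMB reviews data throughout, Table 2 mean-liver-dose limits still bind, every plan is peer reviewed, and hepatic events trigger pembrolizumab holds.

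Most of this stands. It makes the intended reading clear enough to correct with confidence and lowers the importance of the point. It does not remove the conflict: sentence 1 is unconditional, and a dose-release rule should not need inference to apply.

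Two stronger inferences are tempting and unsupported. First, a reader might take 27 of 66 as a measure of how often the conflict would arise. The pairs are unweighted and include outcomes with 8 to 10 severe events in 10 patients. The count also falls to 3 of 66 if grade 3 means grade 3 or higher. Second, a reader might use the ipilimumab and SBRT series in Section 2.2.3, with grade 3 toxicity in 12 of 35, to argue that the missing word would decide dosing. That series used another drug and 50 Gy in 4 fractions, included lung SBRT, and gives no 3-month window for its 34%. It was reported "with no grade 4 or 5 toxicity observed", so it says nothing about the main conflict.

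**Conclusion.** The conflict is real on the face of Section 5.1.2.1. With 0 to 2 grade 3 hepatic toxicities and any grade 4/5 toxicity within 3 months of SBRT, the plan instructs both an increase and no increase. The omission of *hepatic* is a lesser mismatch in the same rule.

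It is a minor safety-rule correction. The consequence of taking the wrong branch is the set of changes in step 4, with the other protections still in place. The documents give no grade 3 or grade 4/5 rate for this combination, so no probability of reaching the conflict can be stated.

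A reader might infer that the plan intends to raise dosing after a grade 4/5 event. The documents do not support that, since the grade 4/5 condition would then serve no purpose. Nor do they show a wider defect in the safety plan or in the response design: the rule does not enter the two-stage test.

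The conclusion assumes only that the two sentences mean what they say and that no other section ranks them; the sections that bear on the rule do not.

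**What to change.** Replace both sentences with one rule, for example:

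> Standard dosing is introduced only if, in the 3 months after SBRT, no more than 2 of the first 10 patients have had grade 3 hepatic toxicity and none has had grade 4/5 toxicity. In every other case the added liver limits stay in force for all patients, and a change to all SBRT constraints is considered.

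This states the precedence, restores *hepatic* to the grade 3 count, and applies one window to both conditions. If the decision has already been taken, a short record of the reading used is enough.

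The drafting cost is negligible. The real cost is waiting. SBRT starts on day 2 and takes 5 to 15 days, so it ends on day 6 to 16. Taking 3 months as 91 days, the tenth patient's window closes on day 97 to 107, which is 12 to 22 days after the nominal 12-week scan (day 85). At 2 to 3 patients a month (Section 13.2), 3 × 2 = 6 to 3 × 3 = 9 patients could enrol while the window runs. With up to 27 planned, at most 17 places follow the tenth patient.

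Those patients would be treated under the tighter limits. Some would receive a lower tumour dose, and one whose mean liver dose is between 15 and 17 Gy at 27.5 Gy could not be treated. The number is smaller if accrual pauses for the stage 1 analysis, which the documents do not state. Part of this wait is already implied, because the existing grade 4/5 condition cannot be ruled out before 3 months.
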